#### 3.4.3 *Blood results*

At each follow-up visit, results for creatinine and therapeutic drug level monitoring will be recorded, as well as a full blood count, lipid profile (total cholesterol, HDL-cholesterol and triglycerides if available) and urinary protein:creatinine ratio at certain visits. These will be copies of results of routine clinical tests requested by the managing team. See Appendix 6: Schedule of study procedures.

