2.3 Tertiary comparisons

The primary outcome will also be assessed in the following subgroups (at 2 years after transplantation and after a median follow-up of 5 years):

- Induction therapy allocation
- Men and women
- Age (<60, ≥60 years)
- Deceased brain death, deceased cardiac death and living donors
- Categories of HLA mismatch defined by NHSBT allocation categories: 1 (no mismatches); 2 (0 DR and 0 or 1 B mismatches); 3 (0 DR and 2B, or 1 DR and 0 or 1 B mismatches); 4 (1 DR and 2B, or 2 DR)
- Sensitization status (high versus normal determined by calculated reaction frequency)
- First and subsequent transplants
- Categories of baseline graft function (eGFR <40, ≥40 <60 and ≥60 mL/min)
- Categories of baseline proteinuria (urine protein:creatinine ratio <30, ≥30 <50, ≥50 mg/mmol)

Exploratory analyses will also be undertaken of reported serious adverse events, non-serious adverse reactions and laboratory results (with due allowance made in their interpretation for the retrospective and exploratory nature of such analyses).

3 Details of analyses

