3.1 Methods of analysis

The fundamental assessments of efficacy and safety will involve comparisons among all randomized patients in their originally allocated treatment group (i.e. “intention to treat” analyses).^{1, 2} Analyses of categorical outcomes will be based on the first relevant unrefuted event of a particular type (i.e. either confirmed or not refuted during the adjudication process). All time-to-event analyses will be based on the first relevant event, and will use log-rank methods to calculate average event rate ratios (95% confidence intervals) and their associated 2-sided P-values.^{2, 4} Comparisons of continuous outcomes will adjust for the baseline value if available, otherwise two-sample t-tests will be used.

The primary comparison between treatment groups of mean follow-up eGFR at 2 years post-transplantation (ie, on average 18 months post maintenance randomisation) will use analysis of covariance (ANCOVA), adjusted for the baseline value.⁵ The baseline creatinine value used will be the latest value available prior to the maintenance randomisation (including a value from a sample

taken on the day of that randomisation). Any value within 6 months of the anniversary of the date of transplantation will be considered as that year's value. If multiple results are available within this window, the one closest to the anniversary date will be used.

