3.2 Missing data

It is likely that values of creatinine will be missing at random (as they will be collected via the UK Transplant Registry and it is very unlikely that their randomized allocation would affect whether a hospital provides data to the registry). Baseline characteristics of those participants with available and those participants with missing data will be compared to identify any characteristics associated with missingness. The amount of missing data at various timepoints after transplantation will be displayed graphically.

Missing eGFR values will be imputed using a multiple imputation model, using baseline covariates of:

- Age (calendar year)
- Sex
- Type of transplant (living donor, donor after brain death and donor after cardiac death)
- Donor age (calendar age)
- Proteinuria at baseline (in categories: ≤ 30 mg/mmol, >30 mg/mmol)
- Available eGFR values (both before and after the value that requires imputation) of creatinine (hence eGFR) will be used as time-varying covariates (as exact values [to 1 decimal place]). Values before the maintenance randomisation will not be considered, nor any values on or after the date of failure of the transplant.
- Any characteristics associated with missingness

The imputation model will be stratified by the induction and maintenance therapy randomized allocations.

20 imputed datasets will be generated and then analysed using methods described in section 3.1.⁶ These 20 results will then be combined in order to produce an overall result using standard procedures.⁷ A complete case analysis will be conducted for comparison, but the primary emphasis will be placed on results after multiple imputation.

Any participant whose transplant has failed will be given an eGFR of 0 mL/min/1.73m² for all analyses after the date of failure. Sensitivity analyses will be conducted to vary this value of eGFR for failed transplants (range 0-10 mL/min/1.73m²). Participants who have died will have eGFR values imputed as for other missing values (and a sensitivity analysis conducted with 0 imputed for any such participants and if such participants are excluded from the analysis).

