Missing values of tacrolimus or sirolimus will also be imputed for any timepoint for which a value is expected but missing. The baseline variables used to impute missing values will include age, sex, type of transplant, donor age and any available values (as exact values to 1 decimal place) that occur after the maintenance randomisation but before failure of the transplant.

Missing values of urine protein:creatinine ratio will be imputed using baseline age, sex, type of transplant, randomized treatment allocations, available PCR values, angiotensin converting enzyme inhibitor or angiotensin receptor blocker use at baseline, diabetes status and cause of kidney

disease. Missing values for lipid fractions will be imputed using baseline age, sex, randomized treatment allocations, PCR at baseline, diabetes status and statin use at baseline.

All multiple imputation analyses will be implemented using SAS procedure MI. The expectation-maximization algorithm (which assumes a multivariate normal distribution) will be used to impute values (as eGFR is a continuous variable with an approximately normal distribution).

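### The imputation model for 2-year eGFR leaves out the baseline eGFR that the primary ANCOVA adjusts for

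*SAP*

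**What the plan says.** SAP 3.1: the primary comparison of 2-year eGFR "will use analysis of covariance (ANCOVA), adjusted for the baseline value". On the baseline itself: "The baseline creatinine value used will be the latest value available prior to the maintenance randomisation". A sample taken on the day of randomisation counts.

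SAP 3.2 lists what enters the imputation of missing eGFR: age, sex, transplant type, donor age, baseline proteinuria in two categories, the available eGFR series, and whatever characteristics prove to be associated with missingness. Baseline eGFR is not named. The item on the eGFR series adds: "Values before the maintenance randomisation will not be considered, nor any values on or after the date of failure of the transplant". Imputation is stratified by both randomised allocations and uses 20 datasets. A complete-case analysis is planned alongside, but "the primary emphasis will be placed on results after multiple imputation".

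Two rules in the same section decide who is imputed. Failed grafts are set to 0. For deaths: "Participants who have died will have eGFR values imputed as for other missing values".

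Protocol 3.4.3 governs how much eGFR exists after the second randomisation: "At each follow-up visit, results for creatinine and therapeutic drug level monitoring will be recorded". Visits at months 9 and 12 fall after that randomisation.

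**The concern.** An imputation model should contain every covariate of the analysis it serves. If it does not, imputed outcomes are drawn as if that covariate carried no information beyond what the other predictors convey. Here the omitted covariate is the one for which the primary ANCOVA adjusts. Protocol 3.5 also treats graft function as prognostic, since the second randomisation is minimised on it.

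Three things could follow for the emphasised result:

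- the ANCOVA slope on baseline is pulled towards zero and the interval widens, possibly beyond that of the complete-case analysis;
- the contrast between the baseline-eGFR subgroups in SAP 2.3 is diluted;
- the treatment difference is biased, if missingness depends on baseline eGFR differently in the two arms.

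**Working it through.** **Can baseline eGFR enter by another route?**

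- The exclusion may be meant only for the time-varying series, because it sits inside that item. Baseline eGFR is still absent from the list, while baseline proteinuria is on it.
- The item on characteristics associated with missingness could admit it, but only if the data show an association, and then against the explicit exclusion.
- A same-day sample counts as baseline in SAP 3.1. SAP 3.2 does not say whether such a value falls before randomisation, so some participants' baselines might be usable and others not.
- The SAP does not apply the bar everywhere. Protein:creatinine ratio is "imputed using baseline age, sex, type of transplant, randomized treatment allocations, available PCR values", with no limit to later values. The drug-level imputation, however, does have that limit.

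None of these reliably puts baseline eGFR into the model.

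**Inputs.** The documents give no figure for the effect of imputation, nor an SD, correlation, missing rate or number at the second randomisation. The power statement in Protocol 2.5 therefore cannot be reproduced exactly. It gives only a bound: a 10 mL/min difference at 75% adherence is 10 × 0.75 = 7.5 mL/min, and with an assumed 400 re-randomised the stated power needs an SD of at most 23.1 (90% at α = 0.05) or 21.9 (80% at α = 0.01). The SD of 18 assumed below is compatible with that.

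**Slope.** With a fraction *m* missing completely at random and equal SDs, the ANCOVA slope after imputation is about (1 − *m*)·ρ + *m*·λ. Here ρ is the baseline to 2-year correlation and λ the slope carried by the imputed records.

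- Only a 12-month value available: λ = r(baseline, 12 months) × r(12 months, 2 years). With 0.80 × 0.85 = 0.68, ρ = 0.75 and *m* = 0.30: 0.70 × 0.75 + 0.30 × 0.68 = 0.73. Simulated: 0.73.
- No post-randomisation value: λ is near 0. With ρ = 0.75 and *m* = 0.30: 0.70 × 0.75 = 0.53 (simulated 0.56). With ρ = 0.70 and *m* = 0.20: 0.80 × 0.70 = 0.56 (simulated 0.58). The small excess comes through the other covariate.

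**Standard error, simulation A.** Assumed: 400 randomised, SD 18, ρ = 0.70; eGFR at 9 and 12 months correlated 0.80 and 0.78 with baseline, and 0.74 and 0.80 with 2 years; one further covariate. Normal-regression imputation within the four allocation cells, 20 imputations, Rubin's rules (total variance = W + (1 + 1/20)B), ANCOVA on baseline, treatment and induction; 1,000 to 1,500 trials per scenario. Increase in SE from leaving baseline eGFR out, by share of missing cases that have interim values:

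| 2-year eGFR missing | All | 90% | Half | None |
|---|---|---|---|---|
| 5% | 0.3% | 1% | 3% | 6% |
| 10% | 0.5% | 2% | 6% | 11% |
| 20% | 1% | 3% | 10% | 18% |
| 20%, ρ from 0.60 to 0.78 | −1 to 5% | 0.5 to 8% | 5 to 17% | 10 to 29% |

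At 20% missing and ρ = 0.70, the SE relative to complete case is 0.99, 1.01, 1.10 and 1.20 across the columns. Coverage is 95 to 97%.

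**Standard error, simulation B.** A 12-month value only; ρ of 0.50, 0.65 and 0.75; 10, 20 and 30% missing. The Rubin SE rises by 0 to 2.5% (all have the value), 0.5 to 5.8% (90%) and 3 to 31% (none). In the middle case (ρ = 0.65, 20% missing) the SE, omitted against included, is 1.496 against 1.489 with the interim value and 1.758 against 1.549 without it. Times 1.96, the half-widths are 2.93 against 2.92 and 3.45 against 3.04 mL/min.

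**Bias.** In A, with a true difference of 5.0, bias is at most 0.1 when missingness depends on baseline equally in both arms. If it does so in one arm only (log-odds 0.5 per SD), bias is −0.1 (all), −0.5 (half) and −1.1 (none), and about 0 with baseline included. In B, arm-dependent missingness gave 9.03 against a true 7.5 with 89% coverage when no interim value existed, and 7.57 when one did. The sign differs between the two set-ups.

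**Subgroup contrast.** With an assumed interaction of 0.2 per mL/min of baseline eGFR and 20% missing, the contrast between eGFR ≥60 and <40 retains 100, 98, 93 and 82% of its size.

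**The case against.** The strongest reply is that the large figures describe situations the plan makes unlikely. At 20% missing, the half and none columns mean 40 and 80 of 400 participants with no creatinine after the second randomisation. Creatinine is recorded at two study visits in that period, with telephone follow-up (Protocol 3.4) and results sought from referring hospitals (Protocol 3.7). Failed grafts are not imputed. A value within 6 months either side of the 2-year date counts, which should limit missing outcomes.

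The SAP also admits eGFR on both sides of the missing value. Adding a 15-month value (assumed correlation 0.83 with 2 years) at 20% missing cut the SE increase from 1.2% to 0.2% when all had interim values, and from 3.2% to about 2.7% when 90% did. The imputed SE was then 0.97 and 0.995 of complete case. Further, the Rubin SE overstates the real loss: in simulation B the empirical SE rose by only 0 to 0.6% with a 12-month value and 1 to 16% without. Missingness that depends on baseline in one arm only sits badly with the SAP's argument that registry reporting does not depend on allocation.

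All of this stands as an argument about size. The half and none columns, the one-arm bias and the subgroup dilution should be read as stress tests. It does not show that baseline eGFR is in the model, nor offer a reason to leave it out.

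**Conclusion.** The concern holds as a free improvement. The imputation model behind the emphasised primary result omits a covariate of its own analysis model. The likely cost is a standard error about 0.3 to 3% larger than necessary, taking 5 to 20% missing, ρ = 0.70 and interim eGFR in at least 90% of missing cases. It grows to 6 to 18% only if no missing case has post-randomisation eGFR; an early death is the clearest individual example. The interval is conservative. The treatment difference stays essentially unbiased unless missingness depends on baseline eGFR differently by arm. All sizes rest on assumed SD, correlations, missing rates and number re-randomised; the omission itself rests on the text alone.

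**What to change.** In SAP 3.2:

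1. List the ANCOVA baseline eGFR, as defined in SAP 3.1 and including a same-day sample, as a continuous covariate of the imputation model.
2. Limit the exclusion sentence to eGFR values earlier than that baseline.
3. State that every covariate of the analysis model is also in the imputation model.

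The cost is SAP wording only, since the value is already collected for the ANCOVA. The change also removes a data-dependent choice about whether baseline eGFR enters the primary imputation.

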### 3.5 **SECOND RANDOMISATION (at ~6 months)**

The second randomisation (between sirolimus- and tacrolimus-based maintenance therapy) can occur from 5 to 7 months post-transplantation (ideally to coincide with 6 month follow-up visit). The following exclusion criteria will apply:

- proteinuria >800 mg/day (or protein:creatinine ratio >80 mg/mmol);
- biopsy-proven acute rejection (Banff score >1) in previous month.

(See section 3.5.1 for guidance on the management of patients who are not willing and eligible for second randomisation or whose local investigator does not consider it in their best interests.)

In order to minimise the impact of this exclusion criterion, investigators will be encouraged to monitor proteinuria and treat it appropriately (with ACE inhibitors and/or angiotensin receptor blockers) during the first six months post-transplant surgery.

The second randomisation will be stratified by induction therapy allocation and minimized by prognostically-relevant criteria including graft function, proteinuria and blood pressure.

Investigators should only randomise patients for whom they remain uncertain about the benefits of CNI-based or sirolimus-based maintenance treatment. Patients with reduced graft function (e.g. eGFR <40 mL/min/1.73m^2) will not be routinely excluded, but their events in this subgroup will be monitored closely by the independent Data Monitoring Committee.

Patients will be allocated to either remain on tacrolimus (all patients to have target trough level 5-7 ng/mL) or convert to sirolimus. The target trough level for sirolimus is 6-12 ng/mL for the first six months (patients who received basiliximab induction should be maintained at the upper end of this range) and thereafter 5-10 ng/mL.

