Campath, Calcineurin inhibitor reduction and Chronic allograft nephropathy

Data Analysis Plan for assessing clinical efficacy and safety of sirolimus-based maintenance treatment in the 3C Study

1 Background

This Data Analysis Plan describes the strategy, rationale and statistical methods that will guide assessment of the clinical efficacy and safety of sirolimus-based maintenance therapy in the 3C Study. A separate Data Analysis Plan will describe the assessment of Campath-based induction therapy. All analyses and reports will be prepared by the coordinating centre in the Clinical Trial Service Unit, University of Oxford.

The 3C Study is a randomized trial investigating two strategies to improve long-term outcomes in kidney transplantation. Firstly, it is comparing Campath (alemtuzumab) with basiliximab as the basis of induction therapy. Secondly, it is comparing an elective conversion to sirolimus-based maintenance therapy at around 6 months after transplantation compared to remaining on tacrolimus-based maintenance therapy. Follow-up visits are scheduled at 1, 3, 6, 9 and 12 months after transplantation and will then be followed by annual mailed questionnaires. In addition, all participants will be flagged with various NHS registries.

2 Comparisons of sirolimus-based versus tacrolimus-based maintenance therapy

All comparisons will involve comparing outcome during the defined analysis period among all those participants allocated at the maintenance randomization to receive sirolimus-based induction versus all those allocated to receive tacrolimus-based maintenance therapy (i.e. “intention-to-treat” analyses).^{1, 2} All analyses will be stratified by induction therapy arm.

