2.2 Secondary comparisons

The secondary comparisons will be of the incidence of the first occurrence (after maintenance randomisation) of:

- i. Graft outcomes:
 - a. Graft rejection

- i. Biopsy-proven acute rejection: cellular (subdivided into Banff 1, 2, 3 and unknown), humoral (subdivided into Banff 1, 2, 3 and unknown) and all³
 - ii. All rejection: presumed and biopsy-proven (as above)
 - b. Graft survival (with reasons for failure subdivided into glomerular disease, fibrosis/atrophy, medical/surgical condition, rejection or unknown)
 - ii. Safety outcomes:
 - a. Serious infections
 - i. All serious infections: subdivided into opportunistic and non-opportunistic
 - ii. Opportunistic infections subdivided into CMV, BK, fungal (non-invasive and invasive) and other (PCP, mycobacterial and other)
 - iii. Non-opportunistic subdivided into urinary tract, respiratory, gastrointestinal, central nervous system, other/unknown
 - b. Cancer
 - i. All cancer: subdivided into haematological (including post-transplant lymphoproliferative disorder and other); skin (subdivided into non-melanoma and melanoma); lung; gastrointestinal; hepatobiliary; breast; prostate; other/unspecified
 - iii. Other outcomes of interest
 - a. Major vascular events (composite of non-fatal myocardial infarction, cardiac death, non-fatal or fatal stroke and arterial revascularisation)
 - b. Death: subdivided into vascular, infection, cancer and other causes
 - c. Composite of death or graft failure
 - d. Post-transplant diabetes mellitus
 - e. Serious adverse events (subdivided into respiratory, gastrointestinal, hepatobiliary, cardiovascular, musculoskeletal, skin, genitourinary, haematological, other transplant-related, other/unspecified)
 - f. Incidence of anaemia (defined as Hb < 13 g/dL in men, <12 g/dL in women) and severe anaemia (defined as Hb <11 g/dL in men, <10 g/dL in women) [at 3 and 6 months post-randomization only]
 - g. Incidence of leucopenia (defined as total white cell count <3 x 10⁹ cells/mm³) [at 3 and 6 months post-randomization only]
 - h. Incidence of neutropaenia (defined as neutrophil count <2 x 10⁹ cells/mm³) and severe neutropaenia (defined as neutrophil count <1 x 10⁹ cells/mm³) [at 3 and 6 months post-randomization only]
 - i. Incidence of thrombocytopaenia (defined as platelet count <75 x 10⁹ cells/mm³) [at 3 and 6 months post-randomization only]
 - j. Levels of immunosuppressants at 3, 6, 12 and 18 months after randomisation

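### The imputation list for missing tacrolimus and sirolimus levels omits both randomised allocations, so imputed early sirolimus levels in the two induction groups are drawn together

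*SAP*

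**What the plan says.** SAP section 3.2 sets out four imputation models.

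- **eGFR:** "The imputation model will be stratified by the induction and maintenance therapy randomized allocations".
- **Urine protein:creatinine ratio:** "Missing values of urine protein:creatinine ratio will be imputed using baseline age, sex, type of transplant, randomized treatment allocations", with further covariates.
- **Lipid fractions:** "Missing values for lipid fractions will be imputed using baseline age, sex, randomized treatment allocations, PCR at baseline, diabetes status and statin use at baseline".
- **Drug levels:** "Missing values of tacrolimus or sirolimus will also be imputed for any timepoint for which a value is expected but missing". The covariates follow: "The baseline variables used to impute missing values will include age, sex, type of transplant, donor age and any available values", limited to levels after the maintenance randomisation and before graft failure. Neither allocation appears.

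All imputation is to use SAS procedure MI under a multivariate normal assumption. Drug levels are item iii.j of SAP section 2.2: "Levels of immunosuppressants at 3, 6, 12 and 18 months after randomisation". SAP section 2 adds: "All analyses will be stratified by induction therapy arm".

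On targets, Protocol section 3.5 gives one sirolimus range, 6-12 ng/mL for the first six months and 5-10 ng/mL afterwards. For the first period it adds that "patients who received basiliximab induction should be maintained at the upper end of this range". The schedule in Appendix 2 (4.2.2) gives the same ranges without that split. The maintenance tacrolimus target is 5-7 ng/mL for everyone.

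**The concern.** When a grouping variable is missing from an imputation model, imputed values in each group are drawn towards a common mean, except to the extent that other covariates carry the group information. Here the protocol gives a reason to expect the induction groups to differ on sirolimus in the first six months after conversion. The only listed covariates that could carry that difference are the patient's other levels.

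At stake is the description of exposure. Readers will use the levels to judge whether treatment was delivered as intended, and possibly to interpret the maintenance result by induction group, which is a pre-specified subgroup for the primary outcome (SAP section 2.3). If early sirolimus levels are imputed as listed, the two induction groups will look more alike than they were.

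**Working it through.** The documents state no figure to reproduce: they give no missing fraction, SD, within-patient correlation or expected difference for drug levels. Everything below is an illustration on assumed inputs.

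**Inputs (assumed).** True induction-group difference *d* = 1 to 3 ng/mL. For scale, if one group averaged the middle of the 6-12 range (9) and the other its top (12), they would differ by 3. SD *s* = 2.5 to 3 ng/mL; correlation between two levels in one patient *r* = 0.3 to 0.6; fraction missing *m* = 10 to 40%; equal induction groups.

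**Formula.** Suppose one other level is available and allocation is not in the model. The regression slope of the missing level on the available one is

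b = (r s² + d²/4) / (s² + d²/4).

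Imputed group means then differ by b·d instead of d, and the fraction of the true difference retained is

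(1 − m) + m·b, with b = 0 when no other level is available.

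**Results at d = 2, m = 20%.**

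| s | r | b | retained |
|---|---|---|---|
| 3 | 0.3 | (2.7 + 1)/(9 + 1) = 0.370 | 0.8 + 0.2 × 0.370 = 87.4% |
| 3 | 0.6 | (5.4 + 1)/10 = 0.640 | 92.8% |
| 2.5 | 0.3 | (1.875 + 1)/(6.25 + 1) = 0.397 | 87.9% |
| 2.5 | 0.6 | (3.75 + 1)/7.25 = 0.655 | 93.1% |
| any | no other level | 0 | 80% |

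Letting *d* run from 1 to 3 (s = 3, r 0.3 to 0.6), the retained fraction is 93-97% at 10% missing, 86-94% at 20% and 73-87% at 40%. With no other level it is 90%, 80% and 60%.

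**Simulation check** (d = 2, s = 3, r = 0.4; 200 patients, 20 imputations, 400 replicates). The formula gives b = (3.6 + 1)/10 = 0.46, so 89.2% at 20% missing and 78.4% at 40%.

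| Imputation model | 20% missing | 40% missing |
|---|---|---|
| No allocation, one other level | 89.5% | 77.4% |
| No allocation, no other level | 80.8% | 59.9% |
| Allocation added, one other level | 101.8% | 99.8% |

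**The maintenance contrast, with each drug imputed separately.** Omitting induction allocation biases the two sirolimus induction groups by equal and opposite amounts when missingness is equal. With d = 2, b = 0.46 and m = 20%, that is ±0.2 × (1 − 0.46) × 1 = ±0.108 ng/mL, which cancels on pooling. The simulated bias in the pooled sirolimus mean was 0.008 ng/mL. With 10% missing in the lower group and 30% in the higher, it was −0.071 ng/mL, falling to 0.001 when induction allocation was added.

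**The maintenance contrast, with both drugs in one level variable.** The same formula then applies to the sirolimus-tacrolimus difference. For example, d = 3, s = 3 and r 0.3 to 0.6 gives 89-94% retained at 20% missing. The SAP does not say that the drugs are combined in this way.

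**Timepoints.** The induction-specific instruction covers the first six months on sirolimus, so it bears on the 3- and 6-month levels. At 12 and 18 months, and for tacrolimus throughout maintenance, the documents set no target that differs by induction group.

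**The case against.** The strongest reply is that the trial's own comparison is hardly touched. A reader might infer that the omission shrinks the sirolimus-versus-tacrolimus exposure difference. The documents do not support that. The two drugs are different analytes with separate targets, and a level is imputed only where one is expected, so imputing each drug on its own largely conditions on maintenance arm. The anticipated 25% stopping sirolimus (Protocol section 2.5) does not rescue that inference: no different tacrolimus target is given for patients who leave sirolimus. It leaves only an uncertainty about when a value counts as expected after a switch. This part of the objection stands.

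It is also true that induction is a stratifier here and not the contrast of interest. Induction has its own analysis plan, and the induction subgroup is specified for the primary outcome only. A comparison of levels between induction groups is therefore a use that readers may make, not a pre-specified analysis. That too stands, and it limits the importance of the point.

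Two further replies carry less weight. The list may not be exhaustive, since the SAP says only what the variables will include; but the authors named allocation for the other three models, so its inclusion cannot be assumed for the fourth. Similarly, the general statement on stratified analyses might be read to cover imputation; but the eGFR model repeats the stratification expressly, and the drug-level paragraph does not. Finally, available levels do carry part of the group information. That makes the attenuation partial, as the calculation shows, but does not remove it.

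**Conclusion.** The point holds in a limited form. The drug-level model is the only one of the four in SAP section 3.2 that names neither allocation. As listed, it attenuates the induction-group difference in sirolimus levels, chiefly at 3 and 6 months after randomisation. At 20% missing the loss is roughly 7 to 13% of a 2 ng/mL difference with another level available, and 20% with none. These sizes rest wholly on assumed values of the difference, SD, correlation and missing fraction; the direction does not depend on their exact values.

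The maintenance contrast is close to unbiased if the drugs are imputed separately and missingness is similar across induction groups. It is attenuated only if the drugs share one variable. The outcome is secondary, and the primary eGFR analysis uses a different imputation model that already conditions on both allocations. This is a free improvement, not a threat to the trial's conclusions.

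**What to change.** Add one sentence to SAP section 3.2: tacrolimus and sirolimus levels are imputed separately, each model including induction and maintenance allocation as covariates. Covariates are preferable to separate runs within allocation groups, because splitting by drug and by both allocations could leave very small cells of patients off their allocated drug. The same sentence should state for which drug a value is expected once a patient has switched, since separate imputation depends on it.

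The cost is a line of text and two model terms. It needs no new data and no change to any other analysis, and it brings this model into line with the other three.
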